5.1 Timing of Analyses

The final analysis will be performed on data transferred to the statistician, having been documented as meeting the cleaning and approval requirements of the database lock and after the finalisation and approval of this SAP document.

There is no interim analysis planned for this study.

5.2 Analysis Populations

5.2.1 Intent-to-treat Population

The Intent-to-treat (ITT) population will consist of all randomized subjects. Analysis will be done according to the randomized treatment. This population will be used for all efficacy analyses.

5.2.2 Safety Population

The safety population will be defined as all randomized subjects who received at least one dose of the medication. Analysis will be done according to the actual treatment subjects received.

5.2.3 Per-Protocol Population

The per-protocol (PP) population will include all subjects who received at least one dose of the medication and who had at least one post-baseline evaluation on the primary endpoint of IGA with no significant protocol deviations. Analysis will be done according to the actual treatment subjects received.

Protocol deviation will be listed and summarized. Prior to database lock, significant protocol deviation will be defined and reviewed in a blinded fashion conjointly by the medical director (or delegate) and the statistician. Patients with significant protocol deviations will be excluded from the PP population.

The PP population will be used for all efficacy analyses as supportive analyses.

5.3 Missing Data/Multiple Observations

No imputation will be done for all population and all parameters, except for the primary endpoint. A supportive analysis using the last observation carried forward (LOCF) method will be performed on responder analysis (see section 7.1 for details).

In the event that two values were collected for the same visit, the scheduled assessment value will be retained in the analyses, unless otherwise specified (e.g. lab error). However, all values will be presented in the data listings. Laboratory values of '< X' or '> X' will be set to 'X' for the analysis.

5.4 Multi-centre Studies

The primary efficacy analysis will be performed with site included in the statistical model as a stratification factor. A sensitivity analysis will also be conducted without site. Analysis on the secondary efficacy endpoints will include information on site. Safety data will be presented with all study sites pooled. Safety analysis will be performed with data from all sites being pooled.

To obtain a sufficient and better-balanced number of subjects among study sites, pooling of study sites will be applied prior to performing the statistical inference and unblinding treatment. Sites without at least 5 subjects in the ITT population will be incorporated into pooled sites as follows:

- All such sites with less than 5 subjects will be ordered from the lowest to the highest in terms of number of ITT subjects. In case of ties, the ordering for tied sites will be determined according to the site identification number (from smallest to largest).
- Sites will be combined beginning at the smallest until the resulting pooled site contains at least 5 ITT subjects. The sites pooled in this way will be considered as a single site in the statistical analyses.
- The process described above will resume for the remaining sites not meeting the criterion of at least 5 subjects. If the final set of pooled site does not meet the criterion of at least 5 ITT subjects, the final set will be pooled with the preceding pooled site.

5.5 Multiple Testing

Since there are only 2 treatment groups involved in this study, no correction for multiplicity will be performed.

6 Summary of Study Data

All continuous variables will be summarised using the following descriptive statistics: n (non-missing sample size), mean, standard deviation (SD), median, inter-quartile range (25th and 75th percentiles), maximum, and minimum. The frequency and percentages (based on the non-missing sample size) of observed levels will be reported for all categorical measures.

In general, all data will be listed, sorted by treatment group, site and subject, and when appropriate by visit number within subject. All summary tables will be structured with a column for each treatment in the same order (DS107G, Placebo) and will be annotated with the total population size relevant to that table/treatment.

Day 0 is the first day of study medication. In the event that there is more than one value for a given assessment prior to the study drug start date, the value obtained closest to Day 0, before administration of study drug will be considered as the baseline value. The baseline value will be the value nearest to and before the first dose of the study medication.

All statistical tests will be two-sided and will be performed with a significant level of 0.05, unless otherwise specified.

6.1 Subject Disposition

Subject disposition information, including the counts and percentages of subjects screened, screen failed, randomized, and who completed the study will be summarized based on all enrolled subjects (i.e. who signed the informed consent form).

Tables will be created indicating the number of subjects by treatment group in each of the analysis populations and attending each visit. Finally, for each of the analysis populations there will be tables indicating by treatment group the number of days in the study, the percentage of subjects discontinued and the reasons for discontinuation. Overall comparability of subject's discontinuation between the two treatment groups will be tested using a Fisher exact test and overall comparability of the reasons for discontinuation for both treatment groups will be done using an exact Pearson's Chi-Squares test.

Number of days in the study will be calculated as the difference between the date of the last visit (Follow up/Week 10) and the informed consent date plus 1.

6.2 Protocol Deviations

Protocol deviations may include, but are not limited to:

- Visit outside of the visit window
- Missed visit
- Missed/Extra dose(s)
- Study Procedure(s) not done
- Prohibited medication
- Etc.

A listing of all protocol deviations will be presented and documented in the study file. A descriptive summary table of protocol deviation categories by treatment group will be presented.

6.3 Demographic and Baseline Variables

Demographic and baseline variables will be analysed using descriptive statistics.

6.4 Medical History

Medical history will be presented using the frequency and percentage of subject by Body System Code.

6.5 Prior and Concomitant Medications

Medications will be coded to the preferred generic name using the WHO-Drug dictionary (version June 2013 B2). Compound product will be coded to the brand name. Any medications that started and ended prior to the study drug start date will be considered as “Prior” and “Concomitant”, otherwise. A listing of all medications will be produced.

6.6 Exposure and Treatment Compliance

Descriptive statistics will be presented by Treatment group on the extent of exposure and the compliance.

The extent of exposure will be defined as:

Number of days on drug = Date of Week 8/ET Visit – First dose study drug administration date.

Compliance will be calculated as follows:

$$\frac{(\text{Sum of all capsules dispensed}) - (\text{Sum of all capsules returned})}{(4 \times \text{Number of days on drug})} * 100$$

7 Efficacy Analyses

All efficacy variables will be summarized using descriptive statistics by treatment group at each visit.

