5.4 Discontinuations

Subjects have the right to withdraw from the study at any time for any reason without penalty. The investigator also has the right to withdraw subjects from the study if he feels it is in the best interest of the subject or if the subject is uncooperative or non-compliant. It is understood by all concerned that an excessive rate of withdrawal can render the study un-interpretable; therefore, unnecessary withdrawal of subjects should be avoided. Should a subject decide to withdraw, all efforts will be made to complete and report the observations, particularly the follow-up examination, as thoroughly as possible.

The investigator or one of his or her staff members should contact the subject either by telephone or through a personal visit to determine as completely as possible the reason for the withdrawal, and record the reason in subject's source document and CRF. A complete final early termination (week 8) evaluation at the time of the subject's withdrawal should be made with an explanation of why the subject is withdrawing from the study. If the reason for removal of a subject is an adverse event or an abnormal laboratory test result, the principal specific event or test will be recorded. Subjects who discontinue the study before week 8 visit will be asked to come for an early termination visit as soon as possible and have the assessments listed at week 8 performed. They will also be asked to return two weeks later for the safety assessments listed at

week 10.

Reasons for discontinuation include:

- The investigator decides that the subject should be withdrawn. If this decision is made because of a serious or persistent adverse event, laboratory abnormality, or intercurrent illness, the study drug is to be discontinued and appropriate measures are to be taken. The investigator will notify the Sponsor or designee immediately.
- The subject or attending physician requests that the subject be withdrawn from the study.
- The subject for any reason requires treatment with another therapeutic agent that has been demonstrated to be effective for treatment of the study indication. In this case, discontinuation from the study occurs immediately upon introduction of the new agent.
- The subject is lost to follow-up, in this case, a reasonable attempt to contact the subject and ascertain his/her status must be made and these attempts must be documented.
- Serious protocol violation, including persistent non-compliance.

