6.1 Treatment Administration

Subjects who fulfill all the inclusion and none of the exclusion criteria may be accepted in the study. Each subject must read and sign an informed consent form prior to any screening procedures being performed. This study involves a comparison of DS107G (2 g) with placebo, administered orally once daily upon waking for a total duration of 8 weeks. The last study drug administration should occur on the day preceding week 8 visit / Early Termination (ET) visit. Subjects will be randomized to one of the two treatment groups in a 1:1 ratio:

- Treatment group A: 2 grams DS107G (4 capsules)
- Treatment group B: 2 grams placebo capsules (4 capsules)

Subjects will be required to start fasting at least 8 hours before drug administration upon waking. Fasting will continue for at least 60 minutes following drug administration, after which subjects can have breakfast. Water will be allowed at all times during the fasting period, but no other fluids will be permitted. Medication(s) for other conditions that are permitted in the study can be taken as usual.

Blister packs will consist of 7 rows of 4 capsules. Each row constitutes one daily dose. Subjects will be instructed to take the 4 capsules **from left to right**, top to bottom, as shown below:

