Serum Chemistry	Albumin, Alkaline Phosphatase, ALT, AST, Chloride, Cholesterol (non-fasting), CK, Creatinine (Enzymatic), GGT, Glucose Random, LDH, Potassium, Sodium, Total Bilirubin, Triglycerides, Urea (BUN), Uric Acid β-hCG for females of childbearing potential (Screening and week 8 / Early termination)
Urinalysis	Blood, Glucose, pH, Protein
Laboratory Tests Required at Screening only	FSH levels for women greater than 40 and less than 60 years of age who have had a cessation of menses for at least 12 months but less than 24 months.

8.2.4 Total and Free DGLA plasma levels, Total Fatty Acid Profile and Interleukins levels

At Baseline, week 4 and week 8 visits, blood draws will be performed prior to study drug administration (no study drug administration at week 8 visit). If a subject comes to the clinic after taking their daily dose of study medication, this subject will be required to come back the following day for PK blood draws. Total DGLA and free DGLA trough plasma levels will be measured. A second blood draw will be performed for later evaluation of total fatty acid profile in plasma. The blood draw for serum chemistry analysis will be split in two aliquots for chemistry analysis and later evaluation of interleukins.

The date and time of the subject's last dose at home before the visit will be recorded accurately. The study site will instruct subjects not to take their daily study drug dose at home for week 4 visit. Dosing will occur in the clinic during the study visit. The exact time of the sample collection must be recorded.

Blood samples will be processed as soon as possible, no later than 1 hour after blood collection. The plasma obtained will be transferred in polypropylene tubes. Each tube will be labeled in order to identify the analyte to be assayed. All samples will be frozen in an upright position. The detailed instruction for PK, Total Fatty Acid and interleukin sample collection, processing, storage and shipment will be provided in the central laboratory manual. The labels on each tube will include at least the following information:

- Study protocol
- Site number
- Subject identification number
- Visit name
- Analyte name
- Primary (A) or Duplicate (B)

Shipment of the experimental samples will be shipped to ICON Central Laboratories.

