Table 14.1.5.3 Summary of Subject Demographics and Baseline Characteristics (Per Protocol Population)

Table 14.1.6
Summary of Medical History
(Safety Population)

Body System	Statistic	Treatment Group		
		DS107G (N=XX)	Placebo (N=XX)	Total (N=XX)
Eyes-Ears-Nose-Throat	n (%)	xx (xx.x)	xx (xx.x)	xx (xx.x)
Respiratory - Asthma	n (%)	xx (xx.x)	xx (xx.x)	xx (xx.x)
Respiratory - Other	n (%)	xx (xx.x)	xx (xx.x)	xx (xx.x)
Cardiovascular	n (%)	xx (xx.x)	xx (xx.x)	xx (xx.x)
Gastrointestinal	n (%)	xx (xx.x)	xx (xx.x)	xx (xx.x)
Hepatobiliary	n (%)	xx (xx.x)	xx (xx.x)	xx (xx.x)
Genitourinary/Renal	n (%)	xx (xx.x)	xx (xx.x)	xx (xx.x)
Reproductive	n (%)	xx (xx.x)	xx (xx.x)	xx (xx.x)
Neurological	n (%)	xx (xx.x)	xx (xx.x)	xx (xx.x)
Endocrinial	n (%)	xx (xx.x)	xx (xx.x)	xx (xx.x)
Hematological	n (%)	xx (xx.x)	xx (xx.x)	xx (xx.x)
Musculoskeletal	n (%)	xx (xx.x)	xx (xx.x)	xx (xx.x)
Dermatological	n (%)	xx (xx.x)	xx (xx.x)	xx (xx.x)
Extremities	n (%)	xx (xx.x)	xx (xx.x)	xx (xx.x)
Immunological	n (%)	xx (xx.x)	xx (xx.x)	xx (xx.x)
Psychiatric	n (%)	xx (xx.x)	xx (xx.x)	xx (xx.x)
Allergies	n (%)	xx (xx.x)	xx (xx.x)	xx (xx.x)

Program: t14_1_6.SAS, Generated on DDMMYY HH:MM

Table 14.1.7.1
Summary of Study Drug Exposure and Compliance
(Safety Population)

Parameters	Statistic	Treatment Group		
		DS107G (N=XX)	Placebo (N=XX)	Total (N=XX)
Number of days on drug	n	xx	xx	xx
	Mean	xx.x	xx.x	xx.x
	SD	xx.x	xx.x	xx.x
	Median	xx.x	xx.x	xx.x
	Min, Max	xx, xx	xx, xx	xx, xx
	Interquartile	xx, xx	xx, xx	xx, xx
Compliance (%)	n	xx	xx	xx
	Mean	xx.x	xx.x	xx.x
	SD	xx.x	xx.x	xx.x
	Median	xx.x	xx.x	xx.x
	Min, Max	xx, xx	xx, xx	xx, xx
	Interquartile	xx, xx	xx, xx	xx, xx

Note(s): Number of days on drug is defined as (Date of Week 8/ET Visit - First dose of study drug administration date)
Compliance is defined as $100 * [(\text{Sum of all capsules dispensed}) - (\text{Sum of all capsules returned})] / [4 \times \text{Number of days on drug}]$

Program: t14_1_7_1.SAS, Generated on DDMMYY HH:MM

Similar tables will be provided for

Table 14.1.7.2 Summary of Study Drug Exposure and Compliance (Intent-to-Treat Population)

Table 14.1.7.3 Summary of Study Drug Exposure and Compliance (Per Protocol Population)

Table 14.2.1.1.1
Summary of Investigator's Global Assessment - Responder Analysis at Week 8
(Intent-to-Treat Population)

Parameter	Statistic	Treatment Group		
		DS107G (N=XX)	Placebo (N=XX)	Total (N=XX)
IGA Score				
Baseline				
3 - Moderate	n (%)	xx (xx.x)	xx (xx.x)	xx (xx.x)

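### Days on drug run to the Week 8/ET visit date, so exposure is overstated and while-on-drug compliance understated when the last dose is more than one day before that visit

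*SAP*

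**What the plan says.** SAP 6.6 sets "Number of days on drug = Date of Week 8/ET Visit" minus the date of first dose. The note to mock Table 14.1.7.1 repeats this: "Number of days on drug is defined as (Date of Week 8/ET Visit - First dose of study drug administration date". Compliance takes the "Sum of all capsules dispensed", subtracts the capsules returned, and divides by four times the number of days on drug. SAP Section 6 adds that "Day 0 is the first day of study medication".

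The planned dosing is in Protocol 6.1: treatment is "administered orally once daily upon waking for a total duration of 8 weeks", and "The last study drug administration should occur on the day preceding week 8 visit / Early Termination (ET) visit".

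Other parts of the documents allow drug to stop earlier than that:
- Protocol 5.4 says that if the investigator withdraws a subject for a serious or persistent adverse event, a laboratory abnormality or an intercurrent illness, "the study drug is to be discontinued and appropriate measures are to be taken". Subjects leaving before Week 8 are asked to attend an ET visit promptly, but no limit in days is given.
- Protocol 9.2 takes a pregnant subject off drug but lets her remain in the study, while Protocol 5.4 lists pregnancy as a reason for discontinuation.
- SAP Listing 16.2.7 codes withdrawal of treatment separately from withdrawal of the subject.

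Protocol 8.2.4 states that the date and time of the "last dose at home before the visit will be recorded accurately". No SAP rule uses that date for exposure.

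**The concern.** A visit date stands in for the end of dosing. It is a good proxy only if the subject took drug until the day before. If drug was stopped earlier, the untreated days between last dose and visit are reported as days on drug and enter the compliance denominator as days on which four capsules were due. A subject who took every capsule until stopping then appears partly non-compliant. A subject lost to follow-up without a Week 8/ET visit has neither an exposure nor a compliance value, because the SAP gives no fallback.

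What is at stake is the accuracy of the exposure and compliance summaries for subjects who stop early. These are the subjects whose actual exposure a reader most wants to know when reading the safety results.

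**Working it through.** **Inputs.** First dose day F = 0 (SAP Section 6). Planned last dose is the day before the visit, once daily for 8 weeks, 4 capsules per day (Protocol 6.1). Week 8 window is Day 56 ± 2 (Protocol 7.5). Drop-out is 10% (SAP Section 4). The gap between last dose and visit is not given anywhere and is assumed below.

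**Formulas.** With L = last dose day and V = visit day:
- SAP days = V − F
- Dosing days = L − F + 1
- Error = V − L − 1
- SAP compliance = 100 × capsules used / (4 × SAP days)

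**Planned case first.** With L = V − 1 the error is 0. A visit on Day 54, 56 or 58 gives 54, 56 or 58 days by either count. At Day 56 this is 56 × 4 = 224 capsules and 224/(4 × 56) = 100%, which reproduces the planned 8 weeks.

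**Early stoppers.** Each subject takes 4 capsules daily until stopping, so compliance while on drug is 100% in every row.

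| Last dose | Dosing days | Visit | SAP days | Error | SAP compliance |
|---|---|---|---|---|---|
| Day 13 | 14 | Day 14 | 14 | 0 | 56/56 = 100% |
| Day 13 | 14 | Day 17 | 17 | +3 | 56/68 = 82.4% |
| Day 13 | 14 | Day 21 | 21 | +7 | 56/84 = 66.7% |
| Day 13 | 14 | Day 28 | 28 | +14 | 56/112 = 50.0% |
| Day 27 | 28 | Day 28 | 28 | 0 | 112/112 = 100% |
| Day 27 | 28 | Day 35 | 35 | +7 | 112/140 = 80.0% |
| Day 27 | 28 | Day 42 | 42 | +14 | 112/168 = 66.7% |
| Day 27 | 28 | Day 56 | 56 | +28 | 112/224 = 50.0% |

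The last row is a subject who stops drug but stays in the study to Week 8.

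**Arm means.** Take 50 subjects: 45 complete 56 days and 5 (10%) stop after 28 dosing days. The true mean is (45 × 56 + 5 × 28)/50 = 53.2 days. If the visit falls g days after the last dose, SAP days for the five are 27 + g:
- g = 3: (2520 + 5 × 30)/50 = 53.4 days; compliance (4500 + 5 × 93.33)/50 = 99.3%
- g = 7: (2520 + 5 × 34)/50 = 53.8 days; compliance (4500 + 5 × 82.35)/50 = 98.2%
- g = 14: (2520 + 5 × 41)/50 = 54.5 days; compliance (4500 + 5 × 68.29)/50 = 96.8%

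The shift is therefore +0.2 to +1.3 days and −0.7 to −3.2 compliance points.

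**Opposite sign.** Protocol 7.5 foresees a subject dosing on the morning of the visit. If the visit date stays Day 56, the error is 56 − 56 − 1 = −1: 57 dosing days are reported as 56, and compliance is 57/56 = 101.8%.

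**The case against.** The strongest defence is that Protocol 6.1 applies its day-before rule to the ET visit as well as to Week 8, so the formula matches the plan. This stands for everyone dosed that way, including an early terminator seen the day after the last dose. A reader might infer that the formula is wrong for all early terminators, and it is not. Protocol 5.4 also asks for the ET evaluation at the time of withdrawal, so gaps are possible but not intended. Even so, a subject taken off drug at once meets the day-before rule only if seen the next day, and the SAP has no rule for any other case.

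A reader might also infer wider consequences, which the documents do not support:
- **Safety rates.** The adverse event tables count subjects against Safety Population totals. No person-time rate and no inferential safety analysis is planned.
- **Per-protocol membership.** SAP 5.2.3 leaves significant deviations to blinded review. Missed and extra doses are deviations in their own right, and no text ties the 6.6 percentage to the PP set. An effect is possible but not established.
- **Between-arm bias.** This would need stopping rates or gaps to differ by arm, and the documents give no figure for either.
- **A larger shift.** A drop of 3.3 to 5 points (10% × 33.3 to 50) requires every drop-out to stop after 14 doses and then be seen only on Day 21 or 28. That is a worst case.

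Two further objections stand. The 100% reference assumes compliance is meant while on drug; counting days after stopping as missed doses is defensible if the SAP says so, though those days would still not be days on drug. And unreturned capsules count as taken, which pushes compliance upward. That is a separate error and does not correct this one.

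**Conclusion.** The point holds in limited form. The SAP formula is exact when the last dose is on the day before the Week 8/ET visit. It overstates exposure and understates while-on-drug compliance when the last dose is earlier than that, and it is undefined without a Week 8/ET visit. For individual subjects the error can be large: 14 dosing days become 21 or 28 under the assumed visit dates. At arm level it is small under the assumptions used (10% stopping after 28 doses, visit 3 to 14 days after the last dose). It touches only descriptive Tables 14.1.7.1 to 14.1.7.3 and Listing 16.2.5.4. No test, adverse event rate or stated PP threshold uses these values. It is worth correcting because a stated rule returns a wrong number for early stoppers and the correction is cheap.

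**What to change.** In SAP 6.6, define days on drug as last dose date − first dose date + 1. The + 1 is needed: without it a fully compliant completer shows 55 days and 224/(4 × 55) = 101.8%. Take the last dose date from the recorded last dose or the compliance log and, if it is unknown, use the last date on which dosing is documented. Use the same value in the compliance denominator and in the note to Table 14.1.7.1, and state that compliance is measured while on drug.

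The cost is one SAP line and one derived date. Protocol 8.2.4 already records the last home dose at the PK visits, Week 8/ET included, and the diary in Protocol 6.3.3 records missed doses. The planned listings do not show a last dose date, so Listing 16.2.5.4 should carry it. The date may be imprecise for subjects lost to follow-up who return no log or capsules, and compliance for them will remain unreliable.

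Separately, Protocol 5.4 and 9.2 differ on whether a pregnant subject leaves the study or only the drug, and must be reconciled.
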